## STUDY SUMMARY

| STUDY OVERVIEW                               |  |
|--|--|
| Full title                                   | Validating neuro-navigated TMS stimulation in SCI patients: a feasibility study towards a gene therapy for SCI.   |
| Objectives                                   | 
Primary objective: Whether neuro-navigated Transcranial Magnetic Stimulation can be used as an additional outcome measure to EM-SCI assessments in a Spinal Cord Injury trial?
 
Secondary objective: Whether nTMS stimulation combined with MRI Tractography can be used as an adjunct outcome tool with EM-SCI assessments for a planned first in human SCI gene therapy trial.
  |
| Type of trial                                | Single site observational study  |
| Trial design and methods                     | Recruited patients will undergo nTMS and MRI Tractography in addition to full EM-SCI assessments. Comparisons will be made to assess the sensitivity of TMS as an outcome measure and whether it can be used as an adjunct whilst assessing SCI patients.  |
| Health condition(s) or problem(s) studied    | Chronic cervical and thoracic spinal cord injuries (greater than 6 months from injury).  |
| Target sample size                           | 20 patients  |
| Trial duration per participant:              | 1 month  |
| Main inclusion/exclusion criteria:           | 
Inclusion Criteria:
 
 
- Single traumatic event at least 6 months prior to recruitment
 
- ISNCSCI grade A, B, C or D
 
- Able to participate in EM-SCI and nTMS assessments and capable of informed consent
 
 
Exclusion Criteria:
 
 
- History of Malignancy
 
- History of other Neurological disease
 
- Pregnancy
 
- Other cord lesions or tethering
 
- Cord transaction or penetrating injury
 
 |
| Statistical methodology and analysis:        | Analysis will be performed in house using SPSS statistical software (IBM SPSS software version 28).  |
| STUDY TIMELINES                              |  |
| Study Duration/length                        | 6 months   |
| Expected Start Date                          | February 2023  |
| End of Study definition and anticipated date | 31 August 2023   |

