## 2 BACKGROUND AND RATIONALE

Worldwide, more than 20 million people live with the devastating consequences of a traumatic SCI, with >250,000 new injuries suffered each year. Along with loss of sensory and motor function and paralysis, many patients suffer incontinence, chronic pain and depression. SCI therefore imposes severe limitations on mobility, independence, full participation in society and quality of life. SCI also has a high financial burden, with healthcare costs among the highest of any medical condition (estimated at £1.4 billion per annum in the U.K.). Current treatments rely on early surgical intervention for mechanical decompression, symptomatic relief, supportive care and rehabilitation. There are currently no adequate therapies available. SCI therefore represents a clear unmet need for which new treatment options are vital.

Most spinal cord injuries occur in the neck (cervical) region, causing upper limb paralysis. Regaining use of the hands (the ability to reach, grip, hold and pick up objects) would enable independent living, is the highest rated patient priority, and would have immense impact for reducing healthcare burden and improving quality of life. King's College Hospital has one of the

largest neurosurgical units in the United Kingdom. It provides specialist acute input for all SCI covering a catchment of over 4 million people. Over the last 5 years it has admitted and treated an average of 65 SCI patients per year, with around half of these patients with a traumatic SCI. KCH's rehabilitation partner is the world-renowned National Spinal Injuries Centre (NSIC) at Stoke Mandeville, and KCH is NSIC's largest referring centre. There is an urgent need to find novel interventions to improve outcome in SCI patients both within our large patient population at King's and also the wider SCI community.

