## ELIGIBILITY CRITERIA

### 5.1 Inclusion Criteria

- Single traumatic event at least 6 months prior to recruitment
- ISNCSCI grade A, B, C or D
- Able to participate in EM-SCI and nTMS assessments and capable of informed consent

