## 10 ADVERSE EVENTS AND INCIDENT REPORTING

### 10.1 Definitions of Adverse Events

| Term  | Definition   |
|---|--|
| Adverse Event (AE)  | Any untoward medical occurrence in a patient or study participant, which does not necessarily have a causal relationship with the intervention/treatment/procedure involved.   |
| Serious Adverse Event (SAE).  | Any adverse event that: 
 
• results in death,
 
• is life-threatening*,
 
• requires hospitalisation or prolongation of existing hospitalisation**,
 
• results in persistent or significant disability or incapacity, or
 
• consists of a congenital anomaly or birth defect
 
 |
| 
*A life- threatening event, this refers to an event in which the participant was at risk of death at the time of the event; it does not refer to an event which hypothetically might have caused death if it were more severe.
 
** Hospitalisation is defined as an in-patient admission, regardless of length of stay. Hospitalisation for pre-existing conditions, including elective procedures do not constitute an SAE.
 |  |

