## 10.4 Procedures for recording and reporting Serious Adverse Events

All serious adverse events will be recorded in the medical records and the CRF.

All SAEs (except those specified in section 16.2 as not requiring reporting to the Sponsor) must be recorded on a serious adverse event (SAE) form. The CI/PI or designated individual will complete an SAE form and the form will be emailed to the R&I Office ([[contact]](mailto:[contact])) within 1 working day of becoming aware of the event.

Where the event is unexpected and thought to be related to the intervention/treatment/procedure this must be reported by the Investigator to the REC and Health Research Authority, using the SAE Report form for non-CTIMPs (available from the HRA website) within 15 days.

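### The hospitalisation footnote in 10.1 does not separate planned or stable-condition admissions from unplanned admissions for worsening, so a study-related worsening of SCI symptoms can be classed as non-serious

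*Protocol*

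**What the plan says.** Protocol 10.1 makes an adverse event serious if it meets any one of several criteria, one being that it requires or prolongs hospitalisation. A footnote to that criterion first defines the term broadly: "Hospitalisation is defined as an in-patient admission, regardless of length of stay". It then takes a class of admissions out: "Hospitalisation for pre-existing conditions, including elective procedures do not constitute an SAE".

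The population is described in the Study Summary as "Chronic cervical and thoracic spinal cord injuries (greater than 6 months from injury"), with a target of 20 patients. Section 5.1 requires "Single traumatic event at least 6 months prior to recruitment". Section 2 says of people living with SCI that "many patients suffer incontinence, chronic pain and depression".

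Section 10.4 attaches two timed reports to serious events. An SAE form goes to the R&I Office within 1 working day. The second, due within 15 days, also goes to the HRA: "Where the event is unexpected and thought to be related to the intervention/treatment/procedure this must be reported by the Investigator to the REC". Section 10.4 exempts SAEs listed in a section 16.2. Section 10.5 discusses SAEs that need not be reported, including disease-related ones.

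**The concern.** An exclusion of this kind usually serves to keep planned surgery and routine care for a stable condition out of the serious-event count. The footnote goes further. The word 'including' makes elective procedures one example of what is excluded, not its limit, so unplanned admissions are covered as well. Nothing in the footnote, or elsewhere in section 10, makes an exception for a condition that has deteriorated since consent or for an admission linked to a study procedure.

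In many studies the clause would touch only some participants. Here the condition under study is itself pre-existing in everyone. What is at stake is timely sight by the sponsor, the REC and the HRA of a temporary but marked deterioration that needs admission after the assessment day. Hospitalisation is the criterion that should catch such an event when no other criterion applies.

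**Working it through.** The point concerns wording, and the plan gives no figure to reproduce. The check follows one hypothetical event through section 10: a participant has an unplanned admission after the assessment day for a worsening of SCI symptoms. The worsening is judged related to a study procedure, is not fatal or life-threatening, and leaves no lasting disability.

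1. **Is it an adverse event?** Yes. The definition in 10.1 opens with "Any untoward medical occurrence in a patient or study participant" and does not exclude worsening of existing disease. Under 10.3 it goes into the medical records and the CRF. Under 10.2 it is assessed for severity, causality, seriousness and expectedness.

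2. **Is it serious by a criterion other than hospitalisation?** No, by construction. Death and threat to life are absent, and the disability criterion, "results in persistent or significant disability or incapacity, or", is not met by a temporary deterioration. Only the hospitalisation criterion remains.

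3. **Does the footnote remove it?** The condition predates consent in every participant (Study Summary, 5.1). The admission is for symptoms of that condition, and there is no exception for worsening. Read literally, it is removed. The footnote does not refer to causality, so a related event is not kept in by being related.

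4. **Do the causality categories prevent this?** Only at the top of the scale. The 'Definitely' category requires other contributing factors to be ruled out, which makes it hard to attribute the admission to the underlying injury. The 'Possibly' category expressly allows the participant's own clinical condition as a contributor. The protocol therefore foresees events that are linked to the condition and still possibly caused by the study. Those are the ones the footnote can remove.

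5. **Which timed reports are lost?** Both routes in 10.4 sit under the heading for serious events. If the event is not an SAE, the 1-working-day form is not triggered, and neither is the 15-day report (which also requires the event to be unexpected).

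6. **Does another part of section 10 restore them?**
   - 10.5 says that unusual frequency or severity must be reported, but this concerns events already classed as SAEs. An event removed by the definition does not clearly come under it.
   - 10.4 points to a section 16.2, but this protocol ends at section 15.
   - 10.5 is template text that tells the author what may be written. It lists no events and gives no rationale.
   - 10.6 applies only if urgent safety measures are taken.
   - 10.8 sends incidents to the Trust through DATIX, not to the REC or HRA.

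The literal path therefore ends with the event in the CRF as a non-serious adverse event and no timed report that is certain to follow.

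**The case against.** The strongest reply is that the footnote need not be read literally. A deterioration triggered by a procedure is a new untoward occurrence, and an investigator could reasonably say that the admission is for that event and not for the stable underlying injury. This stands. The text permits the misclassification but does not direct it. A seriousness definition should still not depend on which of two readings is adopted.

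A reader might infer something stronger: that every such admission is non-serious by rule and can never come to the attention of the sponsor or REC. The documents do not support that. The footnote qualifies only the hospitalisation criterion. All adverse events are recorded and assessed, and urgent safety measures and incident reporting remain open. These routes defeat the word 'never', but none of them guarantees a timed report.

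A reader might also infer that a serious-event rate passed to the planned gene therapy trial would be too low. The protocol plans no such rate. Its objectives carry forward nTMS as an outcome and selection tool, not a safety estimate.

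Nor does the protocol say how likely these admissions are. Participation is a single day of assessments with a non-invasive stimulation method, and the sentence on pain, incontinence and depression describes people with SCI in general, not those enrolled. That limits how much weight the point can bear, but it does not make the wording sound.

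**Conclusion.** The concern holds in a limited form. The footnote in 10.1 is unqualified, and it allows an unplanned admission for a study-related worsening of SCI symptoms to be classed as non-serious when hospitalisation is the only criterion met. That classification takes the event out of both timed routes in 10.4. It does not take it out of the adverse event record.

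The condition that brings the footnote into play is present in 20 of 20 planned participants. That counts who could be affected. It does not count expected admissions or misclassifications, which the protocol gives no basis for estimating.

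The conclusion rests on two assumptions: that the footnote is applied as written, and that the 15-day report in 10.4 is confined to serious events, as its section heading and the form it names indicate. The change should be made because it is small and concerns safety reporting. It is not evidence that an event has been or will be missed.

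**What to change.** Reword the footnote in 10.1 so that the exclusion covers only (a) admissions planned before consent and (b) elective admissions for a pre-existing condition that has not worsened since consent. State that an unplanned admission for worsening of a pre-existing condition after consent, including SCI and its complications, meets the hospitalisation criterion.

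This change is not enough alone, because a worsening newly counted as serious could still be exempted as disease-related under 10.5. So, in the same amendment:

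- In 10.4, replace the reference to section 16.2 with one to a section that exists.
- In 10.5, replace the template text with the sponsor's actual list of exempt events and the rationale, or state that there are none. Make clear that a related and unexpected worsening is not exempt.

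The cost is a short amendment to three adjoining sections, and perhaps a few extra SAE forms for admissions that prove to be unrelated. No assessment, visit or sample size changes.

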### 10.2 Assessments of Adverse Events

Each adverse event will be assessed for severity, causality, seriousness and expectedness as described below.

#### Severity

| Category | Definition   |
|----------|--|
| Mild     | The adverse event does not interfere with the participant's daily routine, and does not require further procedure; it causes slight discomfort                           |
| Moderate | The adverse event interferes with some aspects of the participant's routine, or requires further procedure, but is not damaging to health; it causes moderate discomfort |
| Severe   | The adverse event results in alteration, discomfort or disability which is clearly damaging to health  |

## Causality

The assessment of relationship of adverse events to the procedure is a clinical decision based on all available information at the time of the completion of the case report form.

The following categories will be used to define the causality of the adverse event:

| Category       | Definition   |
|----------------|--|
| Definitely:    | There is clear evidence to suggest a causal relationship, and other possible contributing factors can be ruled out.  |
| Probably:      | There is evidence to suggest a causal relationship, and the influence of other factors is unlikely   |
| Possibly       | There is some evidence to suggest a causal relationship (e.g. the event occurred within a reasonable time after administration of the study procedure). However, the influence of other factors may have contributed to the event (e.g. the participant's clinical condition, other concomitant events). |
| Unlikely       | There is little evidence to suggest there is a causal relationship (e.g. the event did not occur within a reasonable time after administration of the study procedure). There is another reasonable explanation for the event (e.g. the participant's clinical condition).                               |
| Not related    | There is no evidence of any causal relationship.   |
| Not Assessable | Unable to assess on information available.   |

## Expectedness

| Category          | Definition   |
|-------------------|--|
| Expected   | An adverse event which is consistent with the available information about the intervention/treatment/procedure in use in this study.     |
| Unexpected | An adverse event which is not consistent with the available information about the intervention/treatment/procedure in use in this study* |

\* this includes listed events that are more frequently reported or more severe than previously reported

### 10.3 Procedures for recording adverse events

- All adverse events will be recorded in the medical records in the first instance.
- All Adverse events will be recorded in the CRF following consent.
- All adverse events will be recorded with clinical symptoms and accompanied with a simple, brief description of the event, including dates as appropriate.
-

## 10.4 Procedures for recording and reporting Serious Adverse Events

All serious adverse events will be recorded in the medical records and the CRF.

All SAEs (except those specified in section 16.2 as not requiring reporting to the Sponsor) must be recorded on a serious adverse event (SAE) form. The CI/PI or designated individual will complete an SAE form and the form will be emailed to the R&I Office ([[contact]](mailto:[contact])) within 1 working day of becoming aware of the event.

Where the event is unexpected and thought to be related to the intervention/treatment/procedure this must be reported by the Investigator to the REC and Health Research Authority, using the SAE Report form for non-CTIMPs (available from the HRA website) within 15 days.

## 10.5 Serious Adverse Events that do not require reporting

You may choose not to report some particular SAEs to the CI/R&I Office, for example if they are expected to occur on a regular basis and offer no further new information to your safety profile or are related to the disease area of the participants. It should be specified that where the frequency or severity of these events is unusual they must be reported. These events must continue to be recorded in the medical records, CRF however you may state that you will not complete an SAE form and forward it to the CI/R&I Office. Provide the rationale for doing so.

## 10.6 Reporting Urgent Safety Measures

If any urgent safety measures are taken the CI/ PI shall immediately and in any event no later than 3 days from the date the measures are taken, give written notice to the relevant REC, Health Research Authority and R&I office of the measures taken and the circumstances giving rise to those measures.

## 10.7 Protocol deviations and notification of protocol violations

[figure not shown]
A deviation is usually an unintended departure from the expected conduct of the study protocol/SOPs, which does not need to be reported to the sponsor. The CI will monitor protocol deviations.

A protocol violation is a breach which is likely to effect to a significant degree –

- (a) the safety or physical or mental integrity of the participants of the study; or
- (b) the scientific value of the study.

The CI and R&I Office should be notified immediately of any case where the above definition applies during the study conduct phase.

Flow Chart for SAE reporting

## 10.8 Trust incidents and near misses

An incident or near miss is any unintended or unexpected event that could have or did lead to harm, loss or damage that contains one or more of the following components:

- a. It is an accident or other incident which results in injury or ill health.
- b. It is contrary to specified or expected standard of patient care or service.
- c. It places patients, staff members, visitors, contractors or members of the public at unnecessary risk.
- d. It puts the Trust in an adverse position with potential loss of reputation.
- e. It puts Trust property or assets in an adverse position or at risk.

Incidents and near misses must be reported to the Trust through DATIX as soon as the individual becomes aware of them.

A reportable incident is any unintended or unexpected event that could have or did lead to harm, loss or damage that contains one or more of the following components:

- a) It is an accident or other incident which results in injury or ill health.
- b) It is contrary to specified or expected standard of patient care or service.
- c) It places patients, staff members, visitors, contractors or members of the public at unnecessary risk.
- d) It puts the Trust in an adverse position with potential loss of reputation.
- e) It puts Trust property or assets in an adverse position or at risk of loss or damage.

## 11 MONITORING AND AUDITING

The Chief Investigator will ensure there are adequate quality and number of monitoring activities conducted by the study team. This will include adherence to the protocol, procedures for consenting and ensure adequate data quality.

The Chief Investigator will inform the sponsor should he/she have concerns which have arisen from monitoring activities, and/or if there are problems with oversight/monitoring procedures.

## 12 TRAINING

The Chief Investigator will review and provide assurances of the training and experience of all staff working on this study. Appropriate training records will be maintained in the study files

## 13 INDEMNITY ARRANGEMENTS

KCH will provide NHS indemnity cover for negligent harm, as appropriate and is not in the position to indemnify for non-negligent harm. NHS indemnity arrangements do not extend to non-negligent harm and NHS bodies cannot purchase commercial insurance for this purpose; it cannot give advance undertaking to pay compensation when there is no negligence attributable to their vicarious liability. The Trust will only extend NHS indemnity cover for negligent harm to its employees, both substantive and honorary, conducting research studies that have been approved by the R&D Department. The Trust cannot accept liability for any activity that has not been properly registered and Trust approved. Potential claims should be reported immediately to the R&I Office

King's College London holds insurance against claims from participants for harm caused by their participation in this clinical study. Participants may be able to claim compensation if they can prove that KCL has been negligent. However, if this clinical study is being carried out in a hospital, the hospital continues to have a duty of care to the participant of the clinical study. King's College London does not accept liability for any breach in the hospital's duty of care, or any negligence on the part of hospital employees. This applies whether the hospital is an NHS Trust or otherwise.

## 14 ARCHIVING

Research data generated will be stored for up to 5 years following the end of the study. Physical consent forms and some physical personal will also be retained and stored for this time period.

